4.3 Sample Size

This trial requires the test group: ① the non-inferiority comparison with the control groups is established and the next statistical test is carried out; ② when the absolute criteria of SCR and SPR are achieved, the trial can be considered as successful and a positive conclusion can be drawn for the test group. In this trial, when evaluating between the test group 1 (0.25-mL QIV) and test group 2 (0.5mL-QIV), the strategy of sequential test is adopted. First, test group 2 is evaluated. If the positive conclusion of test group 2 is established, test group 1 is further evaluated. Therefore, class I error correction is no longer carried out. The sample size of phase III clinical trials is estimated first by non-inferiority design, namely the QIV group is non-inferior to the TIV group. The primary endpoints of this study include two indicators: SCR and GMT. Only when the SCR and GMT of four serotypes in test group are non-inferior to the control vaccine, the investigational vaccine is considered to be non-inferior to the control vaccine. The total power is 80%, the type II error is 0.2. Based on the different sample size requirements of the two indicators, the type II error is allocated, with 0.16 for SCR comparison and 0.04 for GMT comparison.

(1) Calculation of sample size with the SCR as the indicator:

According to the results of the previous Anflu phase IV clinical trial and other literature, the SCR of the types contained in the vaccine 28 days after vaccination is over 65%, which is used as the reference proportion to estimate the sample size. The test level is taken as one-sided $\alpha=0.025$, the power of non-inferiority comparison for the SCR of a serotype is taken as $1-\beta1/4=1-0.16/4=96\%$, and the non-inferiority threshold Δ is taken as -10%. When comparing the non-inferiority of BY or BV strain, NT:NC=2:1, and PASS software is used to calculate the sample size, the test group needs 914 samples and the control group needs 457 samples. When the non-inferiority test of H1N1 or H3N2 strain is carried out, two control groups are pooled. The sample size ratio of the test group and the pooled control group is 1:1, and the test group and the pooled control group need 625 participants.

(2) Calculation of sample size with the GMT as the indicator:

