6.10 Handling of Missing Data

In mFAS and FAS set analyses, for missing data in the primary estimand under the assumption of Missing at Random, the Multiple Imputation method will be applied to handle missing data before non-inferiority assessment. The imputation will be performed 10 times, with the random seed set to seed=111222333.

For each imputed complete dataset, the following endpoints will be calculated at 28d post-total vaccination for each serotype:

- SCR
- SPR
- GMT (Geometric Mean Titer)
- GMI (Geometric Mean Increase)

The results from all imputed datasets will then be pooled using Rubin's rules to obtain pooled estimates for SCRs, SPRs, GMTs, and GMIs.

Additionally, for the primary estimand in the mFAS analysis set, sensitivity analyses will be conducted under the assumption of Missing Not at Random to evaluate the robustness of the results.

The following methods will be applied:

- TPA (Tipping Point Analysis) method
- δ -adjusted J2R (Jump to Reference) method

Sensitivity Analysis 1: To evaluate the impact of missing values on the primary estimand, TPA will be used for the sensitivity analysis.

- ✓ For the continuous variable, HI antibody, the TPA method will gradually adjust the possible values of the missing data of HI antibody titers of each serotype after logarithmic conversion, 28d post-total vaccination in each group, to find the critical point that reverses the conclusion of GMT analysis. Among them, the smaller the absolute value of the critical point is, the less impact the missing data has on the trial conclusion, and the better the robustness of the trial conclusion is. The Rubin method will be adopted to combine the analysis results of the datasets after each imputation, and the GMT and its 95% confidence interval of each group, as well as the corrected GMT ratio and its 95% confidence interval between each pair of groups (test group 1 / pooled control group, test group 2 / pooled control group) will be obtained through inverse logarithmic transformation. Among them, the number of seeds for multiple imputation will be taken as seed=111222333, and impute 10 times each time.

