- ✓ For the categorical variable, SCR, let the number of subjects with missing HI antibody titers after 28d post-total vaccination in test group 1 that seroconverted in all analysis sets after multiple imputation in main analysis be denoted as n1, and the number of subjects with missing HI antibody titers 28d post-total vaccination in the pooled control group that did not seroconvert in all analysis sets after multiple imputation in main analysis be denoted as n2. The critical point analysis method will sequentially reverse the seroconverted subjects in test group 1 from 0, 1, 2, ..., ni (i = 1, 2) to non-seroconverted, and reverse the non-seroconverted subjects in the pooled control group to seroconverted, to find the critical point that reverses the conclusion of the SCR analysis. The Rubin method will be used to combine the analysis results of each imputed dataset to obtain the pooled SCR, the rate difference between each pair of groups, and their 95% confidence intervals. The seed number for multiple imputations is set as seed = 111222333, and each imputation is performed 10 times. If the confidence interval of the pooled rate or rate difference cannot be estimated, the Bootstrap method is used to estimate the rate or rate difference and their 95% confidence intervals. Bootstrap will perform 1000 times of sampling with replacement, with the seed number set as seed = 111.

In addition, a critical point analysis plot will be drawn to provide a visual basis for result determination.

Using the same method to conduct a sensitivity analysis for test group 2 and the pooled control group.

Sensitivity Analysis 2: To evaluate the impact of missing values on the primary estimand, the δ -adjusted J2R method will be used for sensitivity analysis.

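### As worded, the seroconversion tipping-point search may reverse only missing children with the same imputed status in every imputed dataset, so failing to reach a tipping point would not show robustness

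*SAP*

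**What the plan says.** SAP 6.10 (Handling of Missing Data) plans two missing-not-at-random checks in the mFAS. Sensitivity Analysis 1 is a tipping-point analysis. For SCR it works on children with no titre 28 days after the second dose:

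- The test-arm count is of missing children "that seroconverted in all analysis sets after multiple imputation in main analysis be denoted as n1".
- The control-arm count is of missing children "that did not seroconvert in all analysis sets after multiple imputation in main analysis be denoted as n2".
- The search is capped at those counts. It will "sequentially reverse the seroconverted subjects in test group 1 from 0, 1, 2, ..., ni (i = 1, 2) to non-seroconverted", and does the opposite in the controls.
- On the number of datasets: "The imputation will be performed 10 times, with the random seed set to seed=111222333".

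The text is written for test group 1 against the pooled control. Later sentences in 6.10 extend it to test group 2 and to the BV and BY comparisons. The section does not say what is meant by all analysis sets, what happens when a count is zero, or how an unreached tipping point is to be reported.

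**The concern.** A tipping-point analysis asks how bad the missing outcomes would have to be before the conclusion changes. It informs only if the search can go far enough to include bad cases. Here the eligible children are those whose status is unanimous over ten imputations, that is, those about whom the imputation model is nearly certain. Children with uncertain outcomes, who make up most of the missing data, are never reversed.

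The search would then often end after a few steps. A report of no tipping point would be read as robustness of a co-primary endpoint when it mainly reflects a short grid. The other missing-not-at-random check on SCR, the delta-adjusted jump-to-reference imputation, tests one fixed departure. The tipping-point analysis is the only one that searches a range.

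**Working it through.** **1. Inputs.** From SAP 4.3: the SCR "is over 65%, which is used as the reference proportion to estimate the sample size"; margin -10 points; one-sided alpha 0.025; power 96% per serotype; 1,100 per test group and 550 per control group; dropout about 17%. From SAP 6.10: ten imputations. From SAP 6.8: Miettinen-Nurminen limits for the rate difference. The missing share in the mFAS is not given, so it is assumed: 5% (55 of 1,100) as a working value and 17% (187 of 1,100) as an upper value. The mFAS requires both doses, so its share is probably below 17%.

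**2. The plan's own figure.** Control n = [(z0.975 s0 + z0.96 s1) / 0.10]^2, where s0 uses the restricted null variance (Farrington-Manning) and s1 the variance at 65% in both groups. For 2:1 this gives 456.6, hence 457 control and 914 test. For 1:1 it gives 624.2, hence 625 per group. Both match SAP 4.3. With 17% dropout, 914/0.83 = 1,101, against the stated 1,100. The documents give no figure for the two reversal counts.

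**3. Share eligible, literal reading.** A missing child with imputed seroconversion probability p is eligible with probability p^10 in the test arm and (1-p)^10 in the control arm.

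| SCR | Test, p^10 | Control, (1-p)^10 | Test children of 55 | Test children of 187 |
|---|---|---|---|---|
| 65% | 1.35% | 0.003% | 0.7 | 2.5 |
| 75% | 5.6% | 0.0001% | 3.1 | 10.5 |
| 85% | 19.7% | about 0 | 10.8 | 36.8 |
| 90% | 34.9% | about 0 | 19.2 | 65.2 |

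**4. Letting p vary between children.** A titre-based imputation model was tried with log10 SD 0.7, pre/post correlation 0.2-0.6 and 50-95% susceptible at baseline. At SCR 65% it makes 1.5-6.0% of missing test children eligible (2.7-11.1 of 187) and 0-1.0% of missing controls (0-1.9 of 187). Only very strong separation of children changes this: a beta-binomial correlation of 0.4 gives about 47 test and 10 control children of 187.

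**5. Worked BV case.** Assume 5% missing, 666/1,100 (60.5%) vs 358/550 (65.1%). Miettinen-Nurminen lower limits, treating the imputed data as complete:

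- no reversal: -9.41%
- one test reversal: -9.50%
- six: -9.95%
- seven: -10.05%, and non-inferiority is lost
- full reversal: 55 x 0.605 = 33 test children and 28 x 0.35 = 10 controls, giving -14.19%

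Eligible test children: 55 x 0.605^10 = 0.4 if p is common, or 0.8-3.3 with the titre-based shares of step 4. Eligible controls: about zero. Seven are needed.

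**6. Pooled-control cases, 1,100 vs 1,100.**

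- 65% in both arms, 17% missing: -3.98% at the start. The 2.5 eligible children take it to about -4.2%. A tip needs 66 test reversals. Full reversal (122 test, 65 control) gives -20.96%.
- 60% vs 65%, 17% missing: -9.03% at the start; a tip needs 11; eligible 187 x 0.60^10 = 1.1.
- 80% vs 85%, 17% missing: -8.18% at the start; a tip needs 20; eligible 187 x 0.80^10 = 20.1. Here the restricted search can just tip.
- 65% in both arms, 5% missing: full reversal (36 test, 19 control) gives -8.99%, so there is no tip even without the restriction.

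**The case against.** Four arguments count against the point.

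**The phrase may not mean unanimity.** Elsewhere the SAP uses analysis set for FAS, mFAS and PPS, and calls imputed data imputed datasets. It also orders Rubin pooling over the imputed datasets after reversal, which would fit counting and reversing inside each one. On that reading about 65% of missing test children are eligible (122 of 187) and the restriction disappears. This is possible, but the counts would then differ over ten datasets, while the SAP treats each as one number. A total over the ten datasets is a third reading: 55 x 10 x 0.65 = 358, more than the 55 children missing. The text needs correction on any reading.

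**A reader might infer that the search cannot find a tipping point and reports robustness by construction.** The documents do not support that. The planning value is a floor, and the test share grows quickly above it. At 84% vs 90% (1,100 vs 550, 5% missing) the lower limit is -9.23%, nine test reversals tip it, and 55 x 0.84^10 = 9.6 children are eligible. Even at 65%, a result already very close to -10% can tip.

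**Robustness may be real.** With equal rates of 65% and 5% missing, full reversal does not tip: -8.99% against the pooled control, and just short of -10% against a single control group (679/1,100 vs 368/550 gives -9.99%). The BV example was chosen to start near the margin.

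**The analysis decides nothing.** Immunogenicity is judged primarily on the PPS. The mFAS is complementary, and the jump-to-reference check stresses SCR separately without this restriction. That limits the consequence, but it does not make the tipping-point result informative.

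**Conclusion.** The rule is wrong as written. Read literally, it confines the search to children with unanimous imputed status: at the planning SCR of 65%, about 1-6% of missing test children and 0-1% of missing controls. The control half stays near empty from 65% to 90% unless imputation separates children very strongly. The test half reaches about 20% at 85%, so a tip can occur, but only a small part of the missing-data space is searched. Failure to reach a tipping point would therefore not show robustness. This is a limit on what the analysis can show, not proof that it must always report robustness; with equal rates and 5% or less missing, that report would be correct.

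The figures rest on the literal reading of an undefined phrase, on assumed missing shares of 5% and 17%, and on limits that ignore between-imputation variance. The change should be made because it concerns a co-primary endpoint and costs little, although the analysis has no part in declaring success.

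**What to change.** Redefine the eligible set in SAP 6.10. Let M_T and M_C be the numbers of mFAS children with a missing day-56 titre in the test group and in that strain's comparator: pooled control for H1N1 and H3N2, control group 1 for BV, control group 2 for BY. Run the reversal grid up to the full number missing in each arm, by either route:

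- **Within each imputed dataset**, reversing up to all imputed seroconverters (test) and non-seroconverters (control), then pooling by Rubin's rules; or
- **A deterministic grid**, with k of the M_T missing test children non-seroconverted and the rest seroconverted, and j of the M_C missing controls seroconverted and the rest not. Compute a Miettinen-Nurminen interval in each cell and mark the -10% boundary and the missing-at-random point. Each cell is a complete 2x2 table, so this route needs no pooling or bootstrap.

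Either route is enough. Also state how an unreached tipping point is reported, including the numbers missing and the lower limit at the extreme corner of the grid. The cost is SAP wording and, for the second route, a simpler program. No new data are needed.

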Immunogenicity analyses will be performed primarily based on the Per Protocol Set (PPS), with complementary analyses based on the Full Analysis Set (FAS) and the modified Full Analysis Set (mFAS).

➤ Modified Full Analysis Set (mFAS)

The subject population defined according to intention-to-treat (ITT) principles includes all randomized subjects who have completed the full course of vaccinations, completed blood collection prior to vaccination, and had an effective antibody titer value.

➤ Full Analysis Set (FAS)

The subject population defined according to intention-to-treat (ITT) principles includes all randomized subjects who have completed at least one vaccination, completed blood collection prior to vaccination, and had an effective antibody titer value. Subjects who are administered the vaccine erroneously will be included in the immunogenicity analysis as randomized.

➤ Per Protocol Set (PPS)

It will be a subset of FAS and included all subjects who met the inclusion criteria and did not meet

exclusion criteria, randomized and received full-course vaccination, had a blood sample collected within the time window required by the protocol, and obtained blood sample test results before/after immunization. The subjects who met the following conditions will be excluded from PPS:

- 1) Those who have significant protocol deviations (affecting immunogenicity evaluation).
- 2) Those who are vaccinated with the wrong vaccine.
- 3) Subject received a protocol-prohibited medication/vaccine.
 - Other investigational or unregistered products (drugs or vaccines) that are not investigational vaccines.
 - Use of influenza vaccines other than investigational vaccines.
 - Long-term use (for more than 14 consecutive days) of immunosuppressive or other immunomodulatory drugs (inhaled or topical steroids are allowed).
 - Immunoglobulins or blood products.
- 4) Other conditions that may affect the evaluation of immunogenicity of 28 days after full-course vaccination.

Define the above mFAS, FAS, and PPS for each type (including H1N1, H3N2, BV, and BY), respectively.

(2) Safety Set (SS)

The safety set includes all randomized subjects who have received at least one vaccination. In the safety evaluation, subjects with vaccination erroneously will be included in the statistical analysis based on the actual vaccine groups they received, according to the principle of ASaT (All Subjects as Treated).

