- ✓ If the lower limit of the two-sided 95%CI of SCR difference for 28d post-total vaccination serum HI antibody between the two groups (test group 1-pooled control group) and (test group 2-pooled control group) for this type is $\geq -10\%$, the post-vaccination SCR of the test group for this type can be considered to be non-inferior to that of the pooled control group. Otherwise, the non-inferiority test is considered to have failed.

✧ Analysis of post-vaccination antibody SPR

The post-vaccination antibody SPR in all populations, 28d post-total vaccination serum HI SPR in the susceptible population, and the 28d post-total vaccination serum HI SPR in the non-susceptible population, and the 28d post-total vaccination serum HI SPR in the population of <40 before vaccination, and the 28d post-total vaccination serum HI SPR in the population of ≥ 40 before vaccination under the H1N1 and H3N2 types in test group 1, test group 2, and pooled control group will be analyzed using the same statistical methods as those used for post-vaccination SPR.

If the lower limit of the two-sided 95%CI for the 28d post-total vaccination serum HI SPR of the test group for this type is $\geq 60\%$, this type has reached the absolute standard for SPR.

✧ GMT and GMI analysis

In PPS analysis, the covariance analysis model will be employed to analyze the antibodies under H1N1 and H3N2 types, respectively. After logarithmic transformation, the serum HI GMT 28d post-vaccination will be fitted to the covariance analysis model for analysis, with the serum HI GMT 28d post-vaccination after logarithmic transformation as a dependent variable of the model, the logarithmic transformation value of pre-vaccination serum HI antibody GMT as a covariate of the model, and groups will be the fixed effect in the model. The post-vaccination logarithmic transformation value of each group and the least square mean of the difference between groups will be calculated based on the

model. After inverse logarithmic transformation, the post-vaccination antibody corrected geometric mean based on the least square mean of each group, the corrected ratio between groups (test group 1/pooled control group), (test group 2/pooled control group), (test group 1/test group 2), and their 95%CIs will be calculated.

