In the mFAS and FAS analyses, the missing data in 28d post-total vaccination serum HI antibody will be imputed using the multiple imputation method, and each imputed dataset will be statistically analyzed using the same covariance analysis model as in the PPS analyses. The analytical results of the imputed datasets will be pooled using Rubin's method and inverse-logarithmically transformed to obtain the corrected GMT for each group, corrected GMT ratio between each pair of groups, and corresponding 95%CIs.

If the lower limit of the two-sided 95%CI for (test group 1/pooled control group) and (test group 2/pooled control group) is $\geq 2/3$, the post-vaccination antibody GMT of the test group for this type is considered to be non-inferior to that of the pooled control group. Otherwise, the non-inferiority test is considered to have failed.

The same method as mentioned above will be adopted to perform a logarithmic transformation on the GMT of serum HI antibody in the susceptible population 28d post-total vaccination, and then fit the covariance analysis model for analysis.

Meanwhile, in the PPS analysis, all population, susceptible population, non-susceptible population, population of <40 before vaccination and population of ≥ 40 before vaccination under the H1N1 and H3N2 types in the test group 1, test group 2, and pooled control group will be statistically described in terms of HI antibody GMT and GMI, respectively, and the group differences will be statistically examined by using the ANOVA with logarithmic transformation. Meanwhile, the 28d post-total vaccination antibody's GMT/GMI ratio and corresponding 95%CIs will be calculated for the two groups, and the inter-group difference will be statistically tested by t-test after logarithmic transformation.

In the mFAS and FAS analyses, the missing data in the post-vaccination antibodies will be imputed using the multiple imputation method, and each imputed dataset will be statistically analyzed using the same method as in the PPS analysis. The analytical results of the imputed datasets will be pooled using Rubin's method and inverse-logarithmically transformed to obtain the GMT for each group, the GMI for each group, the GMT ratio between each pair of groups, the GMI ratio between each pair of groups, as well as their corresponding 95%CIs.

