- ✓ For the continuous variable, HI antibody, multiple imputation based on the distribution $N(\bar{X} - 0.176, S_1^2)$ will be performed for missing data of HI antibody titers of each serotype after logarithmic conversion, 28d post-total vaccination in test group 1. Multiple imputation based on the distribution $N(\bar{X}, S_2^2)$ will be performed for missing data of HI antibody titers of each serotype after logarithmic conversion, 28d post-total vaccination in the pooled control group. Here, \bar{X} represents the mean of non-missing log-transformed 28d post-total vaccination HI antibody titers calculated from the pooled control group, S_1 is the standard deviation is calculated from non-missing data in test group 1, and S_2 is the standard deviation is calculated from non-missing data in the pooled control group. The Rubin method will be adopted to combine the analysis results of the datasets after each imputation, and the GMT and its 95% confidence interval of each group, as well as the corrected GMT ratio and its 95% confidence interval between each pair of groups (test group 1 / pooled control group) will be obtained through inverse logarithmic transformation. Among them, the number of seeds for multiple imputation will be taken as seed=111222444, and impute 10 times each time.
- ✓ For the categorical variable, SCR, multiple imputation will be performed based on the Bernoulli(p_1 -0.1) distribution, where p_1 is the SCR calculated from non-missing data in the pooled control group. The Rubin method will be used to combine the analysis results of each imputed dataset to obtain the pooled SCR, the rate difference between each pair of groups, and their 95% confidence intervals. The seed number for multiple imputations is set as seed = 111222555, and each imputation is performed 10 times. If the confidence interval of the pooled rate or rate difference cannot be estimated, the Bootstrap method is used to estimate the rate or rate difference and their 95% confidence intervals. Bootstrap will perform 1000 times of sampling with replacement, with the seed number set as seed = 222.

[figure not shown]
Using the same method to conduct a sensitivity analysis for test group 2 and the pooled control group.

The same method as mentioned above will be used to conduct a sensitivity analysis for the non-inferiority comparison between the BV type and BY type test groups and the control group.

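### The J2R sensitivity analysis of GMT should draw missing titres conditional on the recorded baseline titre that its own covariance model adjusts for

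*SAP*

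**What the plan says.** For GMT, SAP 6.10 (Sensitivity Analysis 2) draws each missing log titre in test group 1 from N(X̄ − 0.176, S1²) and each missing control titre from N(X̄, S2²). X̄ "represents the mean of non-missing log-transformed 28d post-total vaccination HI antibody titers calculated from the pooled control group", and S1 "is the standard deviation is calculated from non-missing data in test group 1". S2 is the control-group counterpart. No term for pre-vaccination titre appears. The same method is extended to test group 2 and to the BV and BY comparisons.

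From the imputed datasets a "corrected GMT ratio and its 95% confidence interval between each pair of groups (test group 1 / pooled control group) will be obtained". SAP 6.8 explains the correction: the GMT model has "the logarithmic transformation value of pre-vaccination serum HI antibody GMT as a covariate of the model", and in the mFAS and FAS "each imputed dataset will be statistically analyzed using the same covariance analysis model as in the PPS analyses".

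SAP section 5 limits the mFAS to "all randomized subjects who have completed the full course of vaccinations, completed blood collection prior to vaccination, and had an effective antibody titer value". The baseline titre is therefore known for the children whose day-56 titre is imputed.

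For SCR, the same analysis uses a Bernoulli draw with probability p1 − 0.1, "where p_1 is the SCR calculated from non-missing data in the pooled control group".

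**The concern.** The imputation leaves out a variable that the analysis conditions on. Imputed titres are unrelated to baseline by construction, so mixing them with observed titres weakens the fitted baseline slope and inflates the residual variance. A missing child with a low baseline also receives a titre typical of the whole control group, which is better than that child's baseline predicts. If such children are lost more in one arm, this unintended gain or loss is added to the intended 0.176 penalty.

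J2R is one of two missing-not-at-random analyses of the primary estimand (the other is the tipping-point analysis). At stake is whether its result can be read as the effect of the stated penalty alone.

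**Working it through.** **Inputs.** From the SAP: log10 SD 0.7, log10 margin −0.176, one-sided alpha 0.025 and 99% power per strain for GMT (4.3); 10 imputations (6.10); results below 1:10 counted as 5 (6.8). The 17% dropout allowance (4.3) serves as an upper value for the missing share f. Not in the documents, so assumed as ranges: the baseline-to-day-56 correlation ρ, and f itself.

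**Step 1. The plan's own figure.** Control n at 2:1 = (1.960 + 2.326)² × 0.7² × 1.5 / 0.176² = 436, hence 872 test; at 1:1 the result is 582. The SAP states 437, 874 and 582, so its SD and margin are confirmed on the log10 scale. The J2R shift is the margin: log10(2/3) = −0.1761.

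**Step 2. Interval width.** With a fraction f of titres unrelated to baseline, the slope shrinks by (1 − f). Within an imputation, the SE relative to baseline-conditional draws is √[(1 − (1 − f)²ρ²)/(1 − ρ²)]. Example, f = 5%, ρ = 0.5: √[(1 − 0.9025 × 0.25)/0.75] = 1.016. Rubin's rules add between-imputation variance, so a simulation was also run: 1,100 v 1,100, bivariate normal, equal true GMTs, covariance model on baseline, 400 runs per cell.

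| Extra SE | ρ = 0.3 | ρ = 0.5 | ρ = 0.7 |
|---|---|---|---|
| 5% missing, formula | 0.5% | 1.6% | 4.6% |
| 5% missing, simulated | 0.7% | 2.4% | 6.8% |
| 17% missing, formula | 1.5% | 5.1% | 14.0% |
| 17% missing, simulated | 2.2% | 6.9% | 18.0% |

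At ρ = 0 there is no meaningful difference. At 1,100 v 550 and 17% missing the simulated figures are 2.2%, 6.9% and 18.1%.

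**Step 3. Shift of the estimate.** Suppose control loss is random and the missing test children average d baseline SDs below their arm's mean. The expected log10 difference is then f × (−0.176 + ρ × 0.7 × d), against the intended f × (−0.176). If they come from the lowest 40% of baselines, d = φ(0.253)/0.40 = 0.386/0.40 = 0.966. At f = 17%:

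| | ρ = 0.3 | ρ = 0.5 | ρ = 0.7 |
|---|---|---|---|
| Formula | +0.005 | +0.028 | +0.051 |
| Simulated, SAP draw | +0.003 | +0.027 | +0.053 |
| Simulated, conditional draw | −0.031 | −0.030 | −0.029 |

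The intended value is 0.17 × (−0.176) = −0.030. When low-baseline children are lost equally in both arms, the SAP draw gives −0.029, −0.031 and −0.030: the shift cancels.

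**Step 4. The floor.** The penalty is cancelled when d exceeds 0.176/(0.7ρ), which is 0.84, 0.50 and 0.36 SD for ρ = 0.3, 0.5 and 0.7. A recorded baseline cannot be below 5. Take log10 baseline as normal with SD 0.7 and values under 10 set to 5. If every missing test child were at the floor, d would be at most 0.82, 0.57 or 0.37 SD with 50%, 70% or 85% of children seronegative (assumed shares).

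In titre terms, with all missing test children at 5, the arm's mean baseline GMT must exceed 5 × 10^(0.176/slope): about 19, 11 and 7.5 for regression slopes of 0.3, 0.5 and 1.0.

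In simulations with a floored baseline, ρ = 0.5 and 5% or 10% missing, seronegative children were made twice as likely to be lost in the test arm only. The mean estimate stayed negative for every seronegative share tried from 30% to 85%.

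**Step 5. Effect on the decision.** At 1,100 v 550, 10% missing, ρ = 0.5, no floor and low-baseline loss in the test arm only, the estimate is +0.013 with lower limit 0.881 as written. With conditional draws it is −0.021 with lower limit 0.819. Imputation under missing-at-random gives a lower limit of about 0.855. With the imbalance reversed, the limits are 0.765 as written and 0.827 conditional. All exceed 2/3.

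**The case against.** Much of the case on the other side stands.

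- Extra width works against declaring non-inferiority. The fix also removes only part of the overstatement. At 17% missing and ρ = 0.5, reported SE against actual sampling SD is 0.0301 v 0.0240 as written and 0.0282 v 0.0239 with conditional draws. The excess falls from 0.0061 to 0.0043, so about 70% remains; it comes from applying Rubin's rules to J2R.
- The mFAS already requires both doses, so the missing share should be below 17%.
- The trial is randomised and double-blind. Nothing in the documents points to loss after the second dose that depends on baseline differently by arm. At ρ = 0.5 with the floor in place, the sign reversed only when essentially all missing test children were seronegative and control loss was random. Even then it did not reverse at 85% seronegative, nor at 70% with 5% missing.
- Immunogenicity is judged mainly on the PPS, which needs both blood results. The tipping-point analysis does not use these draws.

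A reader might infer that the SCR part has the same defect. The documents do not support that: SCR is compared as an unadjusted rate difference, no baseline-adjusted model follows the imputation, and no numerical effect on SCR has been shown.

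One further doubt is that 6.10 does not restate the covariance model, which has to be read from the word corrected and from 6.8. The width result depends on that reading. The shift does not: refitting without the covariate at ρ = 0.5 still gave +0.014 at 10% missing and +0.027 at 17%.

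**Conclusion.** The mismatch in the GMT part is plain in the text. Its certain consequence, provided baseline predicts day-56 titre (which the SAP's own model presupposes), is a modestly inflated SE: about 1-7% at 5% missing and up to about 18% at 17%, for correlations of 0.3 to 0.7. This is conservative. A shifted estimate, including a penalty that is offset or reversed, is conditional on arm-differential loss related to baseline, and the assay floor limits it.

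A reader might infer that the analysis flatters the vaccine in general, or that it could overturn non-inferiority. Neither follows. Equal patterns leave the estimate alone, every lower limit computed stayed above 2/3, and the PPS conclusion does not use these draws. The simulations assumed equal true GMTs; a result already near the margin was not examined. This is a free improvement to a sensitivity analysis.

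**What to change.** In SAP 6.10, Sensitivity Analysis 2, GMT part: regress log10 day-56 titre on log10 baseline titre in the comparator's observed children. Draw missing comparator values from that regression with its residual SD. Draw missing test values from the same regression minus 0.176, with the test-arm residual SD. State in 6.10 that the section 6.8 covariance model is then fitted.

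For SCR, using the comparator's observed rate within baseline stratum (below 1:10; 1:10 or above), minus 0.1 for the test arm, would be consistent with this. It is optional.

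The cost is a few lines of SAP text and code. Every variable is already collected, and the primary analysis does not change.
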